### 3.2.4 Duration of Treatment with Bempegaldesleukin/Pembrolizumab

Accumulating data suggest that 2 years of PD-1 checkpoint inhibitor treatment may be sufficient for long-term benefit. Study CA209003 (NCT00730639), a dose-escalation cohort expansion trial evaluating the safety and clinical activity of nivolumab in patients with previously treated advanced solid tumors (including 129 patients with NSCLC), specified a maximum treatment duration of 2 years. Among 16 patients with NSCLC who discontinued nivolumab after completing 2 years of treatment, 12 patients were alive > 5 years and remained progression-free without any subsequent therapy. In the CA209003 NSCLC cohort, the OS curve begins to plateau after 2 years, with an OS rate of 25% at 2 years and 18% at 3 years ([Brahmer 2017](#)). These survival outcomes are similar to Phase 3 studies in previously treated NSCLC, in which nivolumab treatment was continued until progression or unacceptable toxicity (2 year OS rates of 23% and 29%, and 3 year OS rates of 16%-18% for squamous and nonsquamous NSCLC respectively) ([Felip 2017](#)).

Similar results have been reported in clinical studies of pembrolizumab. KEYNOTE-010 (NCT01905657) was a randomized Phase 3 trial of pembrolizumab (at either 2 mg/kg or 10 mg/kg every 3 weeks) versus docetaxel in patients with previously treated, PD-L1-positive, advanced NSCLC which specified a maximum treatment duration of 2 years for pembrolizumab. OS was significantly longer with both pembrolizumab 2 mg/kg (HR = 0.72, p-value = 0.00017) and pembrolizumab 10 mg/kg (HR = 0.60, p-value < 0.00001) compared to docetaxel, with an

OS plateau developing beyond 2 years in both pembrolizumab arms. Among 690 patients who received pembrolizumab, 47 patients completed 2 years of pembrolizumab and stopped treatment. Most were able to maintain their response, including those with stable disease, with only 2 patients (4%) having confirmed progression after stopping at 2 years ([Herbst 2016](#)).

KEYNOTE-006 (NCT01866319) was a randomized Phase 3 study of pembrolizumab versus ipilimumab in patients with advanced melanoma, which also specified a maximum 2-year duration of pembrolizumab treatment. A total of 104 (19%) of 556 patients randomized to pembrolizumab completed 2 years of treatment. With a median follow-up of 9 months after completion of pembrolizumab, the estimated risk of progression or death was 9% in these patients ([Robert 2017](#)).

Taken together, these data suggest that treatment beyond 2 years is unlikely to confer additional clinically meaningful benefit and that the risk of progression after discontinuing treatment at 2 years is low.

In contrast, a shorter duration of nivolumab of only 1 year was associated with increased risk of progression in previously treated patients with NSCLC, suggesting that treatment beyond 1 year is likely needed. In CA209153 (NCT02066636), patients with previously treated advanced NSCLC who completed 1 year of nivolumab therapy were randomized to either continue or stop treatment, with the option of retreatment upon progression. Among 163 patients still on treatment at 1 year and without progression, those who were randomized to continue nivolumab had significant improvement in PFS compared with those who were randomized to stop treatment, with median PFS (post-randomization) not reached vs 10.3 months, respectively; HR = 0.42 (95% CI, 0.25 to 0.71). With a median follow-up of 14.9 months post-randomization, there also was a trend for patients on continued treatment to live longer (OS HR = 0.63 [95% CI: 0.33, 1.20]). Of note, the PFS curves in both groups plateaued approximately 1 year after randomization (ie, 2 years after treatment initiation), suggesting that there may be minimal benefit in extending treatment beyond a total of 2 years ([Spigel 2017](#)).

Collectively, these data suggest that there is minimal if any benefit derived from continuing immune-oncology treatment beyond 2 years in advanced tumors. However, even though immunotherapy is well tolerated, patients will be at risk for additional toxicity with longer term treatment. Therefore, in this study, the initial treatment will be given for a maximum of 35 cycles (approximately 2 years) following the date of the first dose of study drug.

Given the hypothesis that co-administration of bempegaldesleukin with pembrolizumab will potentiate the pharmacological effects of pembrolizumab, the duration of bempegaldesleukin therapy will also be restricted to 35 cycles (approximately 2 years) to match the duration of pembrolizumab therapy.

### 3.2.5 Justification for Dose

#### 3.2.5.1 Bempegaldesleukin

Bempegaldesleukin 0.006 mg/kg q3w was chosen as the RP2D in the PIVOT-02 study based on the observed clinical safety profile as well as the clinical evidence of a robust immune system activation. Refer to Section 2.1.3.2.2 for additional details regarding the PIVOT-02 study.

#### 3.2.5.2 Pembrolizumab

Pembrolizumab will be given at 200 mg q3w IV according to the label. Based on the totality of data generated in the pembrolizumab development program, 200 mg q3w is the appropriate dose of pembrolizumab across all indications and regardless of tumor type. As outlined below, this dose is justified by:

- Clinical data from 8 randomized studies demonstrating flat dose- and exposure-efficacy relationships from 2 mg/kg q3w to 10 mg/kg every 2 weeks (q2w).
- Clinical data showing meaningful improvement in benefit-risk including OS at 200 mg q3w across multiple indications.
- Pharmacology data showing full target saturation in both systemic circulation (inferred from pharmacokinetic [PK] data) and tumor (inferred from physiologically based PK analysis) at 200 mg q3w.

Among the 8 randomized dose-comparison studies, a total of 2262 patients were enrolled with melanoma and NSCLC, covering different disease settings (treatment naive, previously treated, PD-L1 enriched and all-comers) and different treatment settings (monotherapy and in combination with chemotherapy). Five studies compared 2 mg/kg q3w versus 10 mg/kg q3w (KEYNOTE-001 B2, KEYNOTE-001 D, KEYNOTE-002, KEYNOTE-010, and KEYNOTE-021), and three studies compared 10 mg/kg q3w versus 10 mg/kg q2w (KEYNOTE-001 B3, KEYNOTE-001 F2, and KEYNOTE-006). All of these studies demonstrated flat dose- and exposure-response relationships across the doses studied representing an approximate 5- to 7.5-fold difference in exposure. The 2 mg/kg (or 200 mg fixed-dose) q3w provided similar responses to the highest doses studied. Subsequently, flat dose-/exposure-response relationships were also observed in other tumor types including head and neck cancer, bladder cancer, gastric cancer, and classical Hodgkin Lymphoma, confirming 200 mg q3w as the appropriate dose independent of the tumor type. These findings are consistent with the mechanism of action of pembrolizumab, which acts by interaction with immune cells, and not via direct binding to cancer cells.

Additionally, pharmacology data clearly show target saturation at 200 mg q3w. First, PK data in KEYNOTE-001 evaluating target-mediated drug disposition conclusively demonstrated saturation of PD-1 in systemic circulation at doses much lower than 200 mg q3w. Secondly, a physiologically based PK analysis was conducted to predict tumor PD-1 saturation over a wide

range of tumor penetration and PD-1 expression. This evaluation concluded that pembrolizumab at 200 mg q3w achieves full PD-1 saturation in both blood and tumor.

Finally, population PK analysis of pembrolizumab, which characterized the influence of body weight and other patient covariates on exposure, has shown that the fixed-dosing provides similar control of PK variability as weight-based dosing, with considerable overlap in the distribution of exposures from the 200 mg q3w fixed dose and 2 mg/kg q3w dose. Supported by these PK characteristics, and given that a fixed dose has advantages of reduced dosing complexity and reduced potential of dosing errors, the 200 mg q3w fixed-dose was selected for evaluation across all pembrolizumab protocols.

Additional details on dosing are provided in the pembrolizumab Investigator's Brochure.

### 3.2.5.3 Rationale for Bempegaldesleukin/Pembrolizumab Combination

Accumulating evidence suggests that patients with low baseline CD8+ T cells within the tumor microenvironment (tumor infiltrating lymphocytes [TILs]) predict poor response to checkpoint inhibitor immunotherapies (Daud 2016a; Daud 2016b); thus, agents designed to specifically activate and expand CD8+ T cells may improve clinical outcomes in patients with low TILs. NKTR-214 targets the IL-2 pathway and is designed to provide biased sustained signaling through the heterodimeric IL-2 receptor pathway (IL-2R $\beta\gamma$ ) to preferentially activate NK and effector CD8+ T cells over Treg cells. Preliminary analyses of patients' blood and tumor by flow cytometry and IHC demonstrate that NKTR-214, as a single agent, increases activated CD4+ and CD8+ T cells in peripheral blood, with an increase in T-cell infiltrates within the tumor tissue after 1 dose of NKTR-214. In addition, there is an increase in programmed cell death receptor-1 (PD-1) expression on T cells in the blood and tumor after treatment with NKTR-214. The ability to alter the immune environment and increase PD-1 expression on effector T cells may improve the effectiveness of anti-PD-1/anti-PD-L1 blockade.

## 4.0 STUDY OBJECTIVES AND ENDPOINTS

### 4.1 Primary Objectives and Endpoints

In patients who are aged 18 years and older with recurrent or metastatic HNSCC and positive PD-L1 expression (CPS  $\geq$  1) who have not received prior therapy for the treatment of recurrent or metastatic HNSCC, the primary objectives and endpoints are:

Primary Objective	Endpoint
To compare the overall survival (OS) of bempegaldesleukin plus pembrolizumab versus pembrolizumab monotherapy.	OS, defined as the time from randomization to death due to any cause.
To compare the objective response rate (ORR) of bempegaldesleukin plus pembrolizumab versus pembrolizumab monotherapy.	ORR, defined as the rate of confirmed complete response (CR) or partial response (PR) per Response Evaluation Criteria in Solid Tumors version 1.1 (RECIST 1.1) as assessed by blinded independent central review (BICR).

### 4.2 Secondary Objectives and Endpoints

The secondary objectives and endpoints listed below involve comparison of bempegaldesleukin plus pembrolizumab versus pembrolizumab monotherapy in first-line patients with recurrent or metastatic HNSCC and positive PD-L1 expression (defined by CPS  $\geq$  1) who have not received prior therapy for the treatment of recurrent or metastatic HNSCC:

Secondary Objective	Endpoint
To compare progression-free survival (PFS).	PFS, defined as the time from randomization to the first documented disease progression (per RECIST 1.1 by BICR) or death due to any cause, whichever occurs first.
To compare time to deterioration in global health status/quality of life, pain, and swallowing.	The time from baseline to a $\geq$ 10-point decrease from baseline with confirmation by the subsequent visit of a $\geq$ 10-point deterioration from baseline in: 
 
Global health status/quality of life assessment based on the global health status/quality of life scales of the European Organization for Research and Treatment of Cancer (EORTC) Quality of Life Questionnaire-Core 30 (QLQ-C30).
 
Pain based on the pain multi-item scales of EORTC QLQ head and neck cancer specific module (EORTC QLQ-H&N35).
 
Swallowing based on the swallowing multi-item scales of EORTC QLQ-H&N35.
 

To compare mean change from baseline in global health status/quality of life.	Mean change from baseline in global health status/quality of life scales of EORTC QLQ-C30.
To compare the overall safety and tolerability.	Safety will be based on assessments of treatment-emergent adverse events (AEs) and serious AEs (SAEs).

[Redacted]

[Redacted]	[Redacted]
[Redacted]	[Redacted]
[Redacted]	[Redacted]
[Redacted]	[Redacted]
[Redacted]	[Redacted]
[Redacted]	[Redacted]
[Redacted]	[Redacted]
[Redacted]	[Redacted]
[Redacted]	[Redacted]
[Redacted]	[Redacted]
[Redacted]	[Redacted]
[Redacted]	[Redacted]
[Redacted]	[Redacted]
[Redacted]	[Redacted]
[Redacted]	[Redacted]
[Redacted]	[Redacted]
[Redacted]	[Redacted]

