Primary Objective	Endpoint											
To compare the overall survival (OS) of bempegaldesleukin plus pembrolizumab versus pembrolizumab monotherapy.	OS, defined as the time from randomization to death due to any cause.											
To compare the objective response rate (ORR) of bempegaldesleukin plus pembrolizumab versus pembrolizumab monotherapy.	ORR, defined as the rate of confirmed complete response (CR) or partial response (PR) per Response Evaluation Criteria in Solid Tumors version 1.1 (RECIST 1.1) as assessed by blinded independent central review (BICR).											
Secondary Objective	Endpoint											
To compare progression-free survival (PFS).	PFS, defined as the time from randomization to the first documented disease progression (per RECIST 1.1 by BICR) or death due to any cause, whichever occurs first.											

To compare time to deterioration in global health status/quality of life, pain, and swallowing.
	
The time from baseline to a <math>\geq 10</math>-point decrease from baseline with confirmation by the subsequent visit of a <math>\geq 10</math>-point deterioration from baseline in:
 
 
• Global health status/quality of life assessment based on the global health status/quality of life scales of the European Organization for Research and Treatment of Cancer (EORTC) Quality of Life Questionnaire-Core 30 (QLQ-C30).
 
• Pain based on the pain multi-item scales of EORTC QLQ head and neck cancer specific module (EORTC QLQ-H&N35).
 
• Swallowing based on the swallowing multi-item scales of EORTC QLQ-H&N35.
 

To compare mean change from baseline in global health status/quality of life.
	
Mean change from baseline in global health status/quality of life scales of EORTC QLQ-C30.

To compare the overall safety and tolerability.
	
Safety will be based on assessments of treatment-emergent adverse events (AEs) and serious AEs (SAEs).

[REDACTED]
	

[REDACTED]
	
[REDACTED]

[REDACTED]
	
[REDACTED]

[REDACTED]
	
[REDACTED]

[REDACTED]
	
[REDACTED]

[REDACTED]
	
[REDACTED]

[REDACTED]
	
[REDACTED]

	
[REDACTED]
 
[REDACTED]
 
[REDACTED]
 
[REDACTED]
	
[REDACTED]
 
[REDACTED]
 
[REDACTED]
 
[REDACTED]

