**Arm A (bempegaldesleukin plus pembrolizumab) only:**

- r. See [Appendix 1B](#) for the list of local laboratory tests that require evaluation within 24 hours prior to bempegaldesleukin administration or as soon as locally feasible.
- s. Hydration guidelines provided in [Section 6.2.3.2](#).
- t. See [Section 6.7.1](#) for premedication guidance before study drug infusion(s).
- u. In Cycles 1 and 2, site personnel must contact the patient (by telephone or clinic visit) once between Days 3 and 5 (inclusive) following infusion, to remind the patient of the oral hydration guidelines, to assess for any symptomatology and compliance with the guidelines, and document the results of the discussion (see [Section 6.2.3.2](#)). In Cycles 3 and beyond, the oral hydration follow-up is conducted as clinically indicated for patients in Arm A receiving bempegaldesleukin and pembrolizumab.
- v. Within 5 calendar days following randomization, the patient should receive the first dose of study treatment. Study drug infusion timing should be as close to 30 minutes as possible; however, a window between -5 minutes and +10 minutes is permitted (ie, infusion time is 30 minutes -5 min/+10 min). See [Sections 6.2.2.1](#) and [6.2.2.2](#) for additional details.
- w. At each visit specified, health-related quality of life assessments should be performed in the following order: EQ-5D first, then European Organization for the Research and Treatment of Cancer Quality of Life Questionnaire Core 30 (EORTC QLQ-C30), and finally the EORTC Quality of Life Questionnaire-head and neck cancer specific module (QLQ-H&N35). The questionnaires will be completed prior to dosing at Cycle 1, Cycle 2, Cycle 3, Cycle 4 and every 2 cycles thereafter (eg, Cycle 6, Cycle 8, Cycle 10) up to 1 year from treatment initiation or End of Treatment, whichever occurs first, and at the Follow-up Visit 1. See [Section 9.2](#).
- x. Additional subsequent cancer therapy details such as regimen, setting of the regimen, line of therapy, start date and end date of each regimen, best response to the regimen, and date of progression to subsequent anticancer therapies will be collected.
- y. For Follow-up visits, see [Section 6.3.1](#).
- z. For Survival Follow-up, see [Section 6.3.2](#).

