For the global health status/quality of life and function scales, a higher value indicates a better level of function; for symptom scales and items, a higher value indicates increased severity of symptoms. Prior literature indicates that head and neck pain and the ability to swallow are clinically relevant symptom measures in the recurrent or metastatic HNSCC population ([Bjordal 2000](#); [Chera 2014](#); [Mesia 2010](#); [Machiels 2014](#)). Thus, time to deterioration in the pain and swallowing multi-item scales of the EORTC QLQ-H&N35, in addition to time to deterioration and mean change from baseline in global health status/quality of life scale of the EORTC QLQ-C30, will be evaluated as secondary objectives.

Both the EORTC QLQ-C30 and EORTC QLQ-H&N35 use a recall period of the past week.

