### 11.9.3 Patient-reported Outcome Analyses

Patient-reported outcome (PRO) questionnaires, EORTC QLQ-C30 and EORTC QLQ-H&N35, will be administered by trained site personnel and completed by patients at baseline and throughout the study. It is a best practice and strongly recommended that PROs are administered to randomized patients prior to study drug administration, AE evaluation, and disease status notification.

Global health status/quality of life assessment is based on the global health status/quality of life scales of the EORTC QLQ-C30 (items 29 and 40); pain is based on the pain multi-item scales of the EORTC QLQ-H&N35 (items 31 to 34), and time to deterioration in swallowing (ie, the time from baseline to first onset of PRO deterioration with confirmation), is based on the swallowing multi-item scales of the EORTC QLQ-H&N35 (items 35 and 38). The deterioration in the global health status/quality of life, pain, and swallowing endpoints is defined as a 10 points or greater worsening from baseline for each multi-item scale (Bjordal 2000; Osoba 1998; King 1996) and confirmed by a second adjacent 10 points or more deterioration from baseline under a right-censoring rule.

**Time to PRO deterioration in global health status/quality of life:** defined as time from baseline to the first onset of PRO deterioration with confirmation at the next visit for the global health status/quality of life assessment based on the global health status/quality of life scales of the European Organization for Research and Treatment of Cancer (EORTC) Quality of Life Questionnaire-Core 30 (QLQ-C30).

**Time to PRO deterioration in pain:** defined as time from baseline to the first onset of PRO deterioration with confirmation for pain based on the pain multi-item scales of EORTC QLQ head and neck cancer specific module (EORTC QLQ-H&N35).

**Time to PRO deterioration in swallowing:** defined as time from baseline to the first onset of PRO deterioration with confirmation for swallowing based on the swallowing multi-item scales of EORTC QLQ-H&N35.

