For the above three time to PRO deterioration endpoints, the stratified log-rank test will be used to compare the two treatment arms. A stratified Cox proportional hazards model with treatment as the single covariate will be used to estimate the hazard ratio and corresponding 95% CI, and the Kaplan-Meier method will be used to summarize these time-to-event endpoints per arm, including Kaplan-Meier curves, medians with corresponding 95% CIs, etc.

**Mean change from baseline in global health status/quality of life:** defined as mean changes from baseline in global health status/quality of life assessment based on the global health status/quality of life scales of EORTC QLQ-C30.

To assess the treatment effects on the PRO score changes from baseline in the global health status/quality of life outcome, a constrained longitudinal data analysis (cLDA) model will be applied, with the PRO score as the response variable, and treatment by time interaction, and stratification factors as covariates. Treatment effect on PRO score change from baseline will be primarily evaluated at Week 12. The differences in the least square mean change from baseline will be reported at the primary analysis time point.

Additionally, mean change from baseline in global health status/quality of life will be summarized by visit and the graphs for the mean changes across visits will be provided.

**Changes from baseline in HR-QoL assessments:** Change from baseline in health-related quality-of-life (HR-QoL) assessed by EORTC QLQ-C30 and the EORTC QLQ-H&N35 will be summarized by visit and graphs for mean changes by visit will be provided.

**Opioid analgesic use:** will be measured based on reported concomitant medications. Opioid analgesic use will be summarized descriptively and the mean opioid analgesic use and change from baseline will be plotted across visits.

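### Onset of deterioration in pain and swallowing is defined as a fall in score, although higher is worse on those scales; one QLQ-C30 item number is also out of range

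*Protocol*

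**What the plan says.** Section 4.2 of the protocol lists time to deterioration in three scales as secondary endpoints: the QLQ-C30 global health status/quality of life scale, and the QLQ-H&N35 pain and swallowing scales. One rule covers all three. Onset is at least a "10-point decrease from baseline with confirmation by the subsequent visit of a" deterioration of at least 10 points. The synopsis (Section 1.0) repeats the rule: "decrease from baseline with confirmation by the subsequent visit of a" deterioration of that size.

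Section 9.2.2 gives the score directions. For global health and the function scales, higher is better. But "for symptom scales and items, a higher value indicates increased severity of symptoms", and the same paragraph treats head and neck pain and swallowing as symptom measures.

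Section 11.9.3 defines the event differently. For all three endpoints, deterioration "is defined as a 10 points or greater worsening from baseline for each multi-item scale" and must be confirmed by an adjacent second worsening of at least 10 points. The analysis is attached to that definition: "For the above three time to PRO deterioration endpoints, the stratified log-rank test will be used", with a stratified Cox model for the hazard ratio.

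The same section lists the items behind each scale. The global scale is taken from the "global health status/quality of life scales of the EORTC QLQ-C30 (items 29 and 40"), pain from the "pain multi-item scales of the EORTC QLQ-H&N35 (items 31 to 34"), and swallowing from items 35 and 38.

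**The concern.** A fall in score is a worsening only on the global health scale. On pain and swallowing it is an improvement, so Sections 1.0 and 4.2 start the event with the patient getting better and then require the next visit to confirm that the patient is worse. The two halves of the rule point in opposite directions.

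The formal endpoint definition and the analysis definition therefore identify different patients, and different onset dates, for two secondary endpoints. Someone who programs from the endpoint section and someone who programs from the analysis section would produce different event counts and hazard ratios from the same data.

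The item number is a separate and smaller matter. A scale score is defined by the items that enter it, and one item listed for the global scale appears to belong to the other questionnaire.

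**Working it through.** The plan states no figure to reproduce here, so the check sets the two definitions side by side.

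**Notation.** D1 is the change from baseline at the onset visit and D2 the change at the next visit.

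| Scale | Sections 1.0 and 4.2, as written | Section 11.9.3 |
|---|---|---|
| Global health (higher = better) | D1 ≤ −10 and D2 ≤ −10 | D1 ≤ −10 and D2 ≤ −10 |
| Pain, swallowing (higher = worse) | D1 ≤ −10 and D2 ≥ +10 | D1 ≥ +10 and D2 ≥ +10 |

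For global health the rules agree. For pain and swallowing no pair (D1, D2) meets both, because D1 cannot be both ≤ −10 and ≥ +10. The first rule also needs a swing of at least 10 + 10 = 20 points between adjacent visits.

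**Counting patterns.** On a symptom scale, label each visit F (fall of at least 10 from baseline), N (change of less than 10) or R (rise of at least 10). The Section 4.2 event is F then R at adjacent visits; the Section 11.9.3 event is R then R.

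- Two visits, 3 × 3 = 9 patterns. Section 4.2 counts FR (1). Section 11.9.3 counts RR (1). Shared: 0.
- Three visits, 3 × 3 × 3 = 27 patterns. Section 4.2 counts FRF, FRN, FRR, FFR, NFR and RFR: 3 + 3 = 6. Section 11.9.3 counts RRF, RRN, RRR, FRR and NRR: 3 + 3 − 1 = 5, because RRR arises both ways. Shared: FRR only (1), with onset at visit 1 under Section 4.2 and at visit 2 under Section 11.9.3.

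These are counts of possible patterns, not weighted by how often each would occur.

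**Example on the trial's schedule.** Table 1, footnote w, says: "The questionnaires will be completed prior to dosing at Cycle 1, Cycle 2, Cycle 3, Cycle 4 and every 2 cycles thereafter". With 3-week cycles, Cycle 2 is Week 3, Cycle 3 is Week 6 and Cycle 4 is Week 9. The pain changes below are illustrative.

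| Change at Week 3 / Week 6 | Section 4.2 | Section 11.9.3 |
|---|---|---|
| +15 / +15 (sustained worsening) | no event | event at Week 3 |
| −15 / −15 (sustained improvement) | no event | no event |
| −15 / +15 | event at Week 3, the improved visit | no event, unless Week 9 is again at least 10 worse; then onset is Week 6 |

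**Item number.** The protocol's abbreviation list expands QLQ-C30 as a Core 30 questionnaire, and Section 11.9.3 starts the H&N35 pain items at 31. Item 40 exceeds 30, so it falls in the module's number range and not in the core's. The documents do not give the correct second item.

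**The case against.** The best answer is that the intent is plain and this is a drafting slip. The objective beside the rule is about time to deterioration, and a confirmation clause normally confirms the same event, so *decrease* can be taken as loose wording for worsening. The patient-reported outcomes paragraph of the synopsis describes swallowing neutrally, as first onset of a confirmed deterioration. Section 11.9.3 names all three endpoints, has the right direction and is where the tests are attached. On this view nobody would program the fall-then-rise rule, and the pattern counts measure an unlikely reading.

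Much of this stands. Section 11.9.3 very probably states what was meant, and the counts show only that the two rules are close to disjoint; they do not predict an effect on results. But *decrease* qualifies a number of points, and the same sentence uses *deterioration* separately, so the literal reading is not strained. Section 4.2 is the formal endpoint definition, the synopsis repeats it, and no visible text ranks Section 11.9.3 above it.

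It is also true that the consequence for this trial is negligible. The SAP records that the trial was discontinued and plans only listings for the one patient treated, with no patient-reported outcome summary. That limits the weight of the point but does not correct the definition, and the SAP has no text on these endpoints that would settle the conflict.

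On the item number, the documents never say in words that the core has 30 items; this is inferred from its name and from module numbering that starts at 31. The text was machine-read, so the digit should be checked on the source page. As printed, it is out of range.

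**Conclusion.** The point holds. As written, the endpoint definition of time to deterioration in pain and in swallowing has the wrong direction at onset, contradicts its own confirmation clause and conflicts with Section 11.9.3. This rests only on the score directions in Section 9.2.2 and on reading *decrease* as a fall in points.

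The reach is two secondary endpoints. Global health status/quality of life is unaffected, and no sample size, power or alpha figure depends on the rule. If Section 11.9.3 governs, the planned hazard ratios have the right direction. The item number is one out-of-range entry for one scale and is probably a typing error. The correction should be made, because a formal endpoint definition is wrong as it stands, but its practical consequence for this trial is small.

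**What to change.** In Sections 1.0 and 4.2, replace the onset and confirmation wording with: *worsening of at least 10 points from baseline (a decrease for global health status/quality of life; an increase for pain and for swallowing), confirmed by a worsening of at least 10 points from baseline at the next visit*. This matches Section 11.9.3.

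In Section 11.9.3, correct item 40 and check all the listed item numbers, including those for swallowing, against the scoring manual. No error in the swallowing items is asserted.

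The cost is protocol wording in three sections. The current SAP has no text on these endpoints to change, and neither the design nor the analysis method is affected.
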